Motor performance tests: There are no known risks associated with these tests. They may however be difficult at times, and if the participant becomes discouraged and would like to stop, they can tell the researcher.

Electroencephalography (EEG): Collection of EEG involves application of electrodes over the scalp to measure brain activity. All electrodes do not contact the skin. A gel provides the contact between the skin and the recording electrodes. In rare instances it is possible that the skin may be sensitive to the gel or rubbing alcohol used for surface recordings. In such cases a skin rash is possible. The conductive gel is water-soluble and washes out quickly with warm water and shampoo.

Transcranial magnetic stimulation (TMS): Safety standards for the application of TMS have been developed. Trained operators will follow these standards during this study to minimize the risk. The TMS machine will always be run at a rate and a frequency that are known to be safe. There is a potential risk of causing a seizure in people with a history of seizures (e.g. epilepsy); however, there has never been a report of a seizure associated with the type of TMS used in this study (i.e. single and double pulse TMS). Participants will not be eligible to participate in this study if they have a history of seizure. There is a possible small risk of headache, scalp pain, toothache or scalp numbness associated with single and double pulse TMS. Each of these side effects is transient (i.e. does not last). The clicks associated with single and double pulse TMS are loud and could potentially damage the participant's hearing with prolonged exposures. To minimize this risk, participants will be asked to wear earplugs during the testing session.

There may be other risks that have not yet been identified, and unexpected side effects that have not been previously observed may occur.

Statistical Plan:

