During testing, TMS will be performed using stimulation parameters within established safety guidelines ¹¹. Subject status will be monitored continuously during testing by study staff for potential adverse events. Transient headache and scalp discomfort are the most common adverse effects reported but are not considered serious. If a subject reports either of these events during testing, we will advise participants to follow their typical routine for managing these types of symptoms and to follow up with study staff if any discomfort persists. If persisting symptoms are reported, we will recommend that the subject follow-up with their physician and we will document the event. Contact information for the PI and the Emory University IRB are provided in the consent form. Each subject will receive a copy of the consent form to facilitate reporting of any potential adverse event. In the event that an unforeseen medical emergency should occur, all testing will be conducted in the Center for Rehabilitation Medicine where there is access to emergency medical equipment and a physician present in the building. We will also dial 911 in the case of a medical emergency to provide additional emergency medical services to ensure patient safety and care.

Members of the study team will review study documentation as needed with an informal review scheduled every six months to determine if there are trends for adverse events. If trends are observed, they will be reported to the IRB and the DSMP will be revised to address the presence of these observed adverse events. There are no specific stopping rules for this study. All protocol deviations, adverse events deaths and non-compliance will be reported in accordance with Emory University IRB Reportable Events guidelines.

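### Documentation of headache and scalp discomfort is required only when symptoms persist, so the six-monthly trend review may miss the commonest side effects

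*Combined protocol and SAP*

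**What the plan says.** The relevant text is in two sections of the combined protocol and SAP.

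- **Expected events.** Data Safety and Monitoring states: "Transient headache and scalp discomfort are the most common adverse effects reported but are not considered serious". The TMS paragraph of Risks and Discomforts lists headache, scalp pain, toothache and scalp numbness as a possible small risk, and characterises them thus: "Each of these side effects is transient (i.e. does not last".
- **Observation.** "Subject status will be monitored continuously during testing by study staff for potential adverse events".
- **Response to a symptom in the session.** "we will advise participants to follow their typical routine for managing these types of symptoms and to follow up with study staff if any discomfort" is the first step, with the request to come back to staff applying if the discomfort continues. The second step is: "If persisting symptoms are reported, we will recommend that the subject follow-up with their physician and we will document the event".
- **Cumulative review.** "Members of the study team will review study documentation as needed", together with an "informal review scheduled every six months to determine if there are trends for adverse events". Any trend found goes to the IRB and leads to revision of the monitoring plan. The same section says that the study has no specific stopping rules.
- **Reporting.** A closing sentence commits the study to report adverse events, along with deviations, deaths and non-compliance, under the university IRB's reportable-events guidelines. The content of those guidelines is not reproduced.

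**The concern.** The monitoring plan sets up a review for trends and, a few sentences earlier, a recording rule whose trigger leaves out the course that the expected events normally take. A site that follows the written steps and no more would give the reviewers a record that need not contain the events most likely to occur.

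Two things are at stake. The first is safety oversight. With no stopping rules, the team's own review of documentation, as needed and every six months, is the described route by which a pattern of discomfort would be noticed and acted on. The second is interpretation, to a lesser degree. Real premotor, real M1 and sham stimulation may not feel the same, and a description of discomfort by arm would be useful context beside the primary comparison. Transient symptoms that are not noted at the session are hard to reconstruct later.

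**Working it through.** No arithmetic in the plan bears on this point. The check sets the sentences against one another.

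1. **Where recording is required.** Follow a headache that starts during testing.
   - If it resolves, the stated steps are observation by staff and advice to the participant. No recording step is stated.
   - If it persists and the participant reports this, the stated steps are physician referral and documentation.

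   The second branch is the only place where the protocol expressly says that a symptom will be documented.

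2. **Which branch is expected.** Both sections call these effects transient, so by the protocol's own description the usual case is the first branch.

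3. **What the review reads.** Its stated source is study documentation. No adverse event form, symptom checklist or log is described that would bring first-branch events into that source. Continuous monitoring is an act of observation, and the text names no record arising from it.

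4. **What the rule captures.** Let *n* be the number of symptoms and *p* the share that persist and are reported as persisting. The in-session rule requires documentation of *n* × *p* events and is silent on *n* × (1 − *p*). The documents give neither *n* nor *p*, so no count can be derived. The structural result holds for any *p* below 1.

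5. **Link to stimulation.** Experimental Design has three conditions: real premotor, real M1 and sham over premotor cortex. TMS Procedures gives 80% RMT during training, and 120% RMT plus 30 to 80% of maximum stimulator output before and after the task. No field for condition, site or intensity is attached to a symptom anywhere. The Statistical Plan covers skill scores and cortical excitability and has no safety summary by group.

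6. **Whether the reporting sentence closes the gap.** It concerns what is sent to the IRB, and its scope depends on guidelines outside the documents. Whether they reach expected, non-serious, resolved symptoms cannot be determined. Even on the widest reading, the sentence names no record and no link to site or intensity. On that reading it would also ask for more than the in-session rule provides, so the two need to be reconciled.

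**The case against.** The best reply is that this is silence, not a prohibition. The protocol pairs documentation with referral for persisting symptoms and does not say that other symptoms go unrecorded. It calls headache and scalp discomfort adverse effects, has staff watching for adverse events throughout, and promises to report adverse events, which presupposes some record. This stands against a stronger reading. A reader might infer that resolved symptoms are never recorded and that the review cannot see them or detect a trend. The documents do not support that: good staff practice or the IRB guidelines could fill the gap, and no event rate is given from which to judge whether a trend could be detected. What remains is that the plan does not require the record on which its review depends.

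A reader might also infer that unrecorded discomfort threatens the primary result by slowing responses in one arm. That goes too far. The skill score is random-block performance minus sequence performance. If discomfort adds the same delay *c* to both, then (*R* + *c*) − (*S* + *c*) = *R* − *S*, and the delay drops out of the difference. The high-output input/output blocks are described for participants generally, before and after the task, so they are not a planned difference between arms. Discomfort that interfered with learning itself would not necessarily cancel, but logged symptoms could only describe that possibility. Without a solicited rating from every participant they would not test it.

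Two further points have some force. The effects are described as minor, in healthy adults tested mostly in one session, which limits the consequence. And because a participant receives several intensities in that session, a headache with late onset cannot be assigned to one of them. The record should therefore list what was received and not name a cause.

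**Conclusion.** The point holds as a mismatch between a stated recording trigger and a stated safety review. The protocol does not require resolved headache or scalp discomfort to be documented, so the review may miss the commonest events, and no link to condition, site or intensity is assured. This is more than absent detail, because the trigger that is written down works against the review that is written down.

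The size is qualitative. The conclusion assumes only that staff apply the in-session steps as written and that the expected effects are transient, as the protocol says. It does not depend on any assumed incidence. The clinical consequence is probably modest, and the case for acting rests on the low cost of the remedy. It is not a finding of bias in the primary comparison.

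**What to change.** In Data Safety and Monitoring, replace the documentation clause that applies only to persisting symptoms with wording such as:

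> Every symptom reported or observed during or after stimulation is logged when it occurs, with onset, duration, assigned condition, coil site, and the stimulation blocks and intensities received.

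Then make three consequential edits:

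- State that the existing six-monthly review tabulates these entries by condition.
- Reconcile the sentence on IRB reporting with the log, so that it is clear that all symptoms are recorded and that the IRB guidelines determine which of them are reported.
- Present discomfort by arm beside the primary result as descriptive context only.

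The advice to participants and the physician-referral step need no change; this edit concerns recording alone.

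The cost is one line on the session form and one table at each review, by staff who are already watching participants throughout. The downside is a higher adverse event count than the present rule would yield, which should be explained where the counts are reported.
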